6.1 Selection and number of subjects

Part A

After screening, up to 18 eligible subjects will be enrolled and randomly assigned to DEN-181 or placebo. Sentinel dosing will be included in each dose cohort;

Part B

After screening, up to 40 eligible subjects will be enrolled and randomly assigned to DEN-181 or placebo.

The randomisation numbers will be generated as described in Section 8.1

Subjects enrolled and randomised to treatment in this study are not permitted to be re-enrolled for a second course of treatment.

6.2 Inclusion criteria

The criteria for entry into the study are:

1. Diagnosis of rheumatoid arthritis made by a rheumatologist;
2. HLA-DRB1*0401+, HLA-DRB1*0101+ or HLA-DRB1*0401+HLA-DRB1*0101+ heterozygotes, homozygotes or compound heterozygotes; and ACPA+ (anti-CCP2>6);
3. Treatment with MTX at the same dose for at least 2 weeks prior to planned start of trial treatment;
4. Any swollen joint count at screening (0-28);
5. Age 18-75 years (male or female) inclusive;
6. Patients must be informed of the investigational nature of this study and give voluntary written informed consent in accordance with the institutional and hospital guidelines;
7. Male or Female. Females of child-bearing potential must agree to use two effective forms of contraception from enrolment to completion of the study;
8. Blood glucose, CBC, haemoglobin, platelets, creatinine, bilirubin, and AST/ALT not greater than 1.5 times out of normal range at entry and clinically insignificant in the opinion of the investigator;
9. Patients agree to forego vaccinations during the course of the study;

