Study design:	
Randomised, double-blind, placebo-controlled, single centre, single-dose escalation and multiple dose, dose-ranging parallel group study to be performed in 2 parts.
 
 • Part A: Randomised double blind, placebo-controlled, single centre, single-dose escalation study; • Part B: Randomised double blind, placebo-controlled, single centre, multiple dose, dose-ranging parallel group study at two dose levels.
Number of participants:	
Part A: Total=18 Dose Level 1 (4 active, 2 placebo) Dose Level 2 (4 active, 2 placebo) Dose Level 3 (4 active, 2 placebo)
 
Part B Total=40 Dose Group A (15 active, 5 placebo) Dose Group B (15 active, 5 placebo)

Number of centres:	Single centre
Inclusion criteria:	
 1. Diagnosis of RA made by a rheumatologist; 2. HLA-DRB1*0401+, HLA-DRB1*0101+ or HLA-DRB1*0401+HLA-DRB1*0101+ heterozygotes, homozygotes or compound heterozygotes and ACPA+; 3. Treatment with MTX at the same dose for at least 2 weeks prior to planned start of trial treatment; 4. Any swollen joint count at screening (0-28); 5. Age 18-75 years, inclusive; 6. Male or female. Females of child-bearing potential must agree to use two effective forms of contraception from enrolment to completion of the study; 7. Patients must be informed of the investigational nature of this study and give written informed consent in accordance with the institutional and hospital guidelines; 8. Blood glucose, CBC, haemoglobin, platelets, creatinine, bilirubin, and AST/ALT not greater than 1.5 x out of normal laboratory ranges at entry and clinically insignificant in opinion of investigator; 9. Patients agree to forego vaccinations during the course of the study.

CONFIDENTIAL

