3.2.3 Preclinical safety

A GLP-compliant 22-day repeated dose toxicity study in the Sprague-Dawley rat was undertaken to assess the toxicity and toxicokinetic profile of DEN-181 following 4 once-weekly subcutaneous injections (Days 1, 8, 15 and 22) at low, intermediate and high dose calcitriol (i.e., 0.06, 0.18, and 0.6 µg/animal/dose) and CII peptide (i.e., 4.5, 13.5, and 45 µg/animal/dose). The objective was to assess the persistence, delayed onset or reversibility of any test item-related effects following a 14-day recovery period. Vehicle control, liposomal control, liposomal peptide control, and liposomal calcitriol control items were also administered subcutaneously to groups of rats once weekly (Days 1, 8, 15, and 22).

All main and recovery animals survived until their respective scheduled termination (Day 23 and 36, respectively). Once-weekly subcutaneous injections of DEN-181 at all dose levels in Sprague-Dawley rats for 4 weeks was tolerated and did not result in any signs of overt toxicity. There were no DEN-181-related clinical observations, neurological, autonomic or behavioural effects, nor changes in body weights, food consumption, ophthalmology, hematology, coagulation, urinalysis, organ weights, and macroscopic evaluations that could be attributed to the subcutaneous injection of DEN-181 at any dose level.

Non-adverse dose-related increase in serum calcium and phosphorus levels were noted in DEN-181-treated animals, as well as in liposomal calcitriol control animals at calcitriol levels up to 0.6 µg/animal/dose, but reversed following 14 days of recovery. Microscopically, minimal to moderate renal tubular mineralization in males and females, and minimal mineralization in the stomach glandular mucosa of males were noted, and were attributed to the pharmacodynamic effect of calcitriol up to 0.6 µg/animal/dose with or without collagen II peptide up to 45 µg/animal/dose. The kidney and stomach lesions in males persisted at 0.6 µg/animal/dose of calcitriol (DEN-181 and liposomal calcitriol controls) through the recovery period, while kidney lesions in the females demonstrated reversibility following 14 days of recovery. At this dose, mineralization of renal tubules in males and females and mineralization of the glandular stomach in males were observed, but were minimal in severity, and therefore, considered non-adverse.

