6.4 Other study eligibility criteria considerations

In order to assess any potential impact on subject eligibility with regard to safety, the Investigator must refer to the relevant document(s) for detailed information regarding warnings, precautions, contraindications, adverse events, and other significant data pertaining to the study product being used in the study. Such documents may include, but not limited to the Clinical Investigator's Brochure (IB) or equivalent document provided by the Sponsor.

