7.4.3 Blood and urine samples for laboratory tests

Blood and urine will be collected at all visits and should be within the visit window (see 7.2) Detailed instructions on the handling and processing of specimens are located in the Study Reference Manual. The following will be collected at the times specified in Section 7.3:

Haematology:	Haemoglobin, haematocrit, red blood cell (RBC) count , white blood cell and differential white blood cell count, platelet count, mean corpuscular volume (MCV), mean corpuscular haemoglobin concentration (MCHC), erythrocyte sedimentation rate (ESR).
Chemistry:	Sodium, potassium, chloride, bicarbonate, BUN, creatinine, total protein, albumin, serum amylase, phosphorus, AST, ALT, GGT, alkaline phosphatase, total bilirubin, glucose, CPK, calcium, uric acid, C-reactive protein (CRP)
Viral Serology:	HIV, HCV and HBV (at screening). HIV testing will be repeated after screening if there is a clinical suspicion that a subject may be at risk of infection.
Immunological:	HLA typing if required. HLA typing does not need to be repeated if part of medical record from an appropriately accredited laboratory, anti-CCP2 titre (if required), Rheumatoid Factor, Tetramer analysis (Collagen II peptide and other RA autoantigens), Exploratory immune assays (measures of humoral and T cell responses e.g. Interferon-gamma (IFN- γ) enzyme linked immunospot (ELIspot) assays, T-cell responses specific for RA autoantigens)
Urinalysis:	Protein, glucose, blood and microscopy (if abnormal).
Urine Pregnancy:	Human chorionic gonadotropin.
Serum pregnancy:	Human chorionic gonadotropin.
Pharmacokinetics:	Calcitriol concentration in plasma and pharmacokinetic indices

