10.6 Toxicity Management

AEs and abnormal laboratory values, if appropriate, should be graded according to the NCI CTCAE v4.03 grading scale (Appendix 1). Where parameters are not addressed within the TGS, laboratory abnormalities should be assessed as “Clinically Significant” or “Not Clinically Significant”. All abnormal values should be confirmed by repeat testing as soon as possible, preferably within 3 calendar days of receipt of results prior to dose interruption or discontinuation, unless such a delay is not consistent with good medical practice.

For the purpose of monitoring toxicities, the baseline value is defined as the last value prior to the administration of the first dose of study product. This value must be obtained from the local laboratory. All management is based on changes from this value.

All results that are classified as “Clinically Significant” should be documented in the AE form of the CRF.

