12.3 Withdrawal of subjects from study product

Investigational medicinal product is administered once during Part A of this protocol and three times during the conduct of Part B of this protocol.

Section 10.7 provides guidance for dose modification or discontinuation of IMP in the event of AEs or abnormal laboratory values.

If a subject permanently discontinues dosing with IMP, for example as a result of an AE, every attempt should be made to keep the subject in the study and continue to perform the required study related follow-up and procedures.

The ideal is to continue to follow the subject for the full study period or until resolution of the adverse event. If it is not possible for the subject to remain in the study for the full study period, every attempt should be made to keep the subject in the study up to the Exit Evaluation at Day 57. If the subject remains in the study but off study treatment, all study procedures should continue as per protocol.

If the subject will not remain in the study for all study related procedures, the Exit Evaluation should be performed wherever possible.

All subjects who discontinue study medication dosing should be followed for at least 30 days after the last dose of IMP in order to monitor subjects for possible post-treatment events which may occur after IMP has been discontinued.

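### The entry criteria set no serum calcium limit, although DEN-181 delivers calcitriol and calcium and albumin are already measured at screening

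*Protocol*

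**What the plan says.** Criterion 8 in Protocol 6.2 reads "Blood glucose, CBC, haemoglobin, platelets, creatinine, bilirubin, and AST/ALT not greater than 1.5 times out of normal range at entry and clinically insignificant", subject to the Investigator's opinion. The synopsis repeats it with the same analytes, ending "creatinine, bilirubin, and AST/ALT not greater than 1.5 x out of normal laboratory ranges at entry and clinically insignificant in opinion of investigator". The exclusions in 6.3 and the Part B criterion in 6.3.1 do not mention calcium, hypercalcaemia or any disorder of calcium metabolism.

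On the product, 3.2.3 reports for the rat study: "Non-adverse dose-related increase in serum calcium and phosphorus levels were noted in DEN-181-treated animals". It adds that renal tubular mineralisation in both sexes and gastric mineralisation in males "were attributed to the pharmacodynamic effect of calcitriol".

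On measurement, the chemistry panel in 7.4.3 includes "total protein, albumin, serum amylase, phosphorus, AST, ALT, GGT, alkaline phosphatase, total bilirubin, glucose, CPK, calcium, uric acid". By 7.3.1 and Table 1-1 this panel is drawn at screening and at every later visit.

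On handling after entry, 10.6 takes the last value before the first dose as baseline and states "All management is based on changes from this value". On exposure, 12.3 states "Investigational medicinal product is administered once during Part A of this protocol", and three times in Part B.

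**The concern.** The protocol puts entry limits on analytes such as glucose and bilirubin, but not on the one that its own animal data tie to an active ingredient. Two candidates with the same raised calcium could be treated differently, because no stated rule applies to both.

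Safety is the primary objective, laboratory abnormalities are part of the primary endpoint (4.2.1), and 10.8 describes the study as first in man. At stake is whether a patient who starts with raised calcium is given calcitriol, and whether that patient's later values are then judged against an already abnormal reference. An entry limit belongs in the protocol, so the point is not one that the SAP could settle.

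**Working it through.** **1. Limited against measured.** Criterion 8 limits glucose, CBC, haemoglobin, platelets, creatinine, bilirubin and AST/ALT. The screening panel in 7.4.3 measures calcium, albumin and phosphorus as well, and none of these has an entry limit. The nearest exclusions (malignancy, another active inflammatory disease, significant renal disease) remove some candidates but are not calcium limits. Section 9 records vitamin supplements without restricting them.

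**2. What stands before the first dose.**
- 6.4 obliges the Investigator to consult documents such as the Investigator's Brochure when judging eligibility on safety grounds.
- 10.5 requires the Investigator to review all laboratory values in real time and asks that clinically significant abnormalities go to the Medical Monitor.
- Section 6 bars exemptions from the criteria. It does not oblige the Investigator to enrol everyone who meets them.
- Day 1 chemistry is sampled before dosing, but 7.3.2 does not say that the result must be available first. The screening result is therefore the dependable one.

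These are routes for judgement. None is a stated calcium threshold.

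**3. What stands after the first dose.**
- Under 10.6 a raised pre-dose calcium becomes the management reference. CTCAE grading still applies.
- Part A has one dose, so the rules in 10.7 act only after the exposure.
- In Part B, 10.7 requires safety assessments immediately before each dose and stops dosing if laboratory changes pose a significant health risk. Doses 2 and 3 can therefore be withheld.

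**4. Patients and doses.** Inputs are from 5.1 and 5.2.
- Part A active: 3 × 4 = 12 patients, 12 × 1 = 12 doses.
- Part B active: 2 × 15 = 30 patients, 30 × 3 = 90 doses.
- Total active: 12 + 30 = 42 of 58 patients, 12 + 90 = 102 doses.
- Maximum calcitriol per patient: 1 × 0.6 = 0.6 µg in Part A, 3 × 0.6 = 1.8 µg in Part B.

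**5. The stated margin.** Section 3.3 gives a human equivalent of 0.093 µg/kg at the rat NOAEL.
- Mean rat dose at the NOAEL: (0.45 + 0.71)/2 = 0.58 µg/kg, as stated.
- Maximum human dose at 70 kg: 0.6/70 = 0.0086 µg/kg.
- Margin: 0.093/0.0086 = 10.8, which reproduces the stated figure of about 11.
- Lower Part A levels at 70 kg: 0.093/(0.06/70) ≈ 108 and 0.093/(0.18/70) ≈ 36. Only 4 of the 12 active Part A patients receive 0.6 µg.

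**6. Frequency of raised calcium.** The documents give none. For illustration only, assume 0.5% to 3% of otherwise eligible candidates:
- Part A active patients: 12 × 0.005 = 0.06 to 12 × 0.03 = 0.36.
- Extra screen failures per 58 candidates: 58 × 0.005 = 0.3 to 58 × 0.03 = 1.7.

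**7. Why not add calcium to criterion 8.** With an assumed upper limit of 2.5 to 2.6 mmol/L, the 1.5-times allowance would admit 1.5 × 2.5 = 3.75 to 1.5 × 2.6 = 3.9 mmol/L. That would be no useful limit.

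**The case against.** The strongest reply is that this is a preference and not a defect. The protocol says nothing false here and no analysis is affected. Real-time laboratory review, Medical Monitor input, mandatory consultation of the safety documents, the creatinine limit and the renal and malignancy exclusions already narrow the gap. The Brochure, which is not at hand, may advise on calcium. The doses are small and the rat calcium rises were called non-adverse and reversed. All of this stands, and it keeps the point minor. It does not supply a common rule, since each of the general safeguards ends in case-by-case judgement.

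A reader might infer that entry is the only safeguard for all 42 active patients. The documents do not support that: for the 30 in Part B, later doses can be stopped. A reader might also infer that raised calcium would go unseen once it is the baseline. That does not follow either, because chemistry is repeated at every visit and values are still graded under CTCAE.

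A limit at the upper limit of normal is also open to the charge of bluntness, since it has no tolerance for trivial excursions. Retesting under 6.4.3 helps only partly: it covers abnormalities inconsistent with previous history and needs Sponsor agreement. This objection is fair, and the fix below carries its own repeat clause for that reason.

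**Conclusion.** The omission is real and worth correcting, at low severity. No criterion limits serum calcium in a study of a calcitriol-containing product whose rat data show a calcium effect, although the screening panel already provides the measurement. The consequence is sharpest for the 12 active Part A patients, for whom entry is the only point at which exposure can be prevented. It is weaker for the 30 active patients in Part B.

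The absolute risk is low on the documents' own figures. The documents do not support a claim that the dose is unsafe, or that any given number of patients with raised calcium would be enrolled: the counts above rest wholly on an assumed 0.5% to 3%. The conclusion assumes only that the Brochure leaves the decision to judgement. If it already sets a calcium limit, that limit should be copied into 6.2.

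**What to change.** Add a separate criterion to 6.2 and to the synopsis, outside the 1.5-times rule: *Screening albumin-corrected serum calcium not above the laboratory upper limit of normal; one out-of-range value may be repeated during screening and the repeat used.* The sponsor's medical team should confirm the threshold.

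The cost is one line in each place, with no new test or visit. The downside is a few extra screen failures, about 0.3 to 1.7 per 58 otherwise eligible candidates under the assumed frequencies. The repeat clause should reduce that number. It matters somewhat in a single-centre study already restricted by HLA type, ACPA status and methotrexate treatment.

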6.3 Exclusion criteria

The criteria for exclusion from the study are:

1. Malignancy;
2. An active inflammatory disease other than RA;
3. Currently receiving or have received treatment with >10mg prednisone daily within the last 2 weeks prior to screening;
4. Current or recent treatment (< 2 weeks prior) with any disease-modifying anti- rheumatic drugs other than methotrexate;
5. Serious infection requiring hospitalization within last 28 days;
6. Receipt of any live attenuated vaccines within 4 weeks prior to entry;
7. Major surgery within last 28 days;
8. Significant cardiovascular, renal, liver, neurological or skin disease;
9. Positive serology for HIV or infection with HBV or HCV;
10. Treatment with cytotoxic or immunomodulatory therapies such as radiotherapy, cyclophosphamide, mycophenolate, tacrolimus, PUVA, acitretin, cyclosporine or azathioprine;
11. Any known or suspected allergies to the study drug or its constituents including egg products;
12. Inadequate venous access to allow collection of blood samples;
13. History of drug or alcohol abuse;
14. Participation in another clinical study;
15. If, in the opinion of the PI, the subject appears not to be able to perform the needed responsibilities of participation in the clinical study.

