Exclusion criteria:	
 1. Malignancy; 2. An active inflammatory disease other than RA; 3. Currently receiving or have received treatment with >10mg prednisone daily within the last 2 weeks prior to screening; 4. Current or recent treatment (< 2 weeks prior) with any disease-modifying anti-rheumatic drugs (DMARDS) other than MTX; 5. Serious infection requiring hospitalisation within last 28 days; 6. Receipt of any live attenuated vaccines within 4 weeks prior to entry; 7. Major surgery within last 28 days; 8. Significant cardiovascular, renal, liver, neurological or skin disease; 9. Positive serology for HIV, or infection with HBV or HCV; 10. Current treatment with cytotoxic or immunomodulatory therapies such as radiotherapy, cyclophosphamide, mycophenolate, tacrolimus, PUVA, acitretin cyclosporine or azathioprine; 11. Any known or suspected allergies to the study drug or its constituents including egg products; 12. Inadequate venous access to allow collection of blood samples; 13. History of drug or alcohol abuse; 14. Participation in any other clinical trial; 15. If, in the opinion of the PI, the subject appears not to be able to perform the needed responsibilities of participation in the clinical study.
Part B Specific Inclusion Criteria	Diagnosis of RA made by a rheumatologist within the previous 2 years.
Investigational Product:	DEN-181 is a suspension of egg phosphatidylcholine (EPC) and egg phosphatidylglycerol (EPG) liposomes (approx. 100 nm diameter, lipid molar ratio 90:10) containing collagen II peptide and calcitriol in 2 mL amber glass vials for single use. Each vial contains 1.0 mL extractable volume of DEN-181 containing 0.6 µg/mL calcitriol and 45µg/mL collagen II peptide.
Comparator:	Placebo is sterile saline for injection (0.9% NaCl).
Duration of treatment per participant:	
Screening: Up to 21 days Study period: 56 days
 
Subjects will receive either: Part A- a single administration of DEN-181 with 56 days (8 weeks) of post treatment follow up or Part B- three administrations of DEN-181 at weekly intervals with 42 days (6 weeks) of post treatment follow up (on study period of up to 11 weeks for each participant from the start of Screening to the end of follow-up)

CONFIDENTIAL

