7.3.1 Visit 1 Screening visit

Subjects will be screened within 35 days prior to randomisation to determine eligibility for participation in the study. The following will be performed and documented at Screening:

- Obtain written informed consent. (This must be completed prior to any other procedure)
- A screening medical history (see Section 7.4.1)
- A complete physical examination including: (see Section 7.4.1)
 - Vital signs
 - Bodyweight
 - Height
 - Assessment of all appropriate body systems to determine study eligibility
- Electrocardiogram (See section 7.4.2)
- Concurrent medication assessment (See Section 9)
- Blood samples for
 - Haematology including ESR (See section 7.4.3)
 - Clinical chemistry including CRP (See section 7.4.3)

- Viral serology for HIV, HBV and HCV (See section 7.4.3)
- Pregnancy testing (See Section 7.4.6)
- Blood samples for immunological assessments including:
 - HLA typing (if not already part of the participant's medical record; see Section 7.4.3)
 - Anti-CCP2 titre (See Section 7.4.3)
 - Rheumatoid Factor (See Section 7.4.3)
- Urine samples for urinalysis (see Section 7.4.2)
- DAS28CRPv4 evaluation (See section 7.4.7)

Subjects meeting the inclusion criteria and none of the exclusion criteria will return to the clinic within 35 days after screening for randomisation. If the patient misses randomisation and requires rescreening within a new 35 day window, blood samples for hematology and clinical chemistry including CRP, and pregnancy testing (if relevant) only are required to be repeated. The other laboratory and clinical data from the previous screen may be used, and updated with any relevant medical history/examination and medications.

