7.3.2 Visit 2 (Day 1) baseline evaluations, randomisation, and study medication dispensing

At Visit 2 the following tests will be performed and documented on the Case Report Form (CRF) prior to administration of the IMP:

- Review of inclusion/exclusion criteria (see Section 6.2 and 6.3)
- Urine samples for urinalysis and pregnancy testing (see Section 7.4.3 and 7.4.6)
- A complete physical examination (see Section 7.4.1)
- Vital signs (see Section 7.4.1)
- Concurrent medication assessment (see Section 9)
- Adverse event questioning (see Section 10)
- DAS28CRPv4 evaluation (see section 7.4.7)
- Blood samples for:
 - Haematology including ESR (see Section 7.4.3)
 - Clinical chemistry including CRP (see Section 7.4.3)
- Blood samples for immunological assessments including (See sections 7.4.3 and 7.4.4):
 - Tetramer analysis (Collagen II and HA)
 - Exploratory Immune assays
- Blood samples for calcitriol concentration assessment (See Section 7.4.3)
- An oral swab will be (See Section 7.4.8)

Once the above assessments have been performed the patient will be randomised and the IMP will be administered.

- Subjects will be observed and vital signs will be measured at 15 and 30 minutes following the administration of IMP
- Subjects will remain in the clinic for at least four hours post-administration of IMP
- Blood samples for calcitriol concentration assessment will be taken 1, 2 and 4 hours after IMP administration

- The subject will be issued with an Injection Site Reaction Diary and instructed to view their injection site (s) at the same time each day and record their findings every day for 3 days.(See Section 7.4.5)

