9.2 Concurrent medications/treatments not permitted

9.2.1 Prior to study entry

Refer to exclusion criteria in Section 6.3 with particular note to the following medications and treatments that are not permitted:

- Currently receiving >10mg prednisone/day;
- Receipt of any live attenuated vaccines within 4 weeks prior to entry;
- Treatment with cytotoxic or immunomodulatory therapies such as radiotherapy, cyclophosphamide, mycophenolate, tacrolimus, PUVA, acitretin, cyclosporine or azathioprine;
- Concurrent treatment or treatment within 2 weeks of trial commencement with any DMARD other than MTX;
- Other investigational drugs.

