9.2.2 During the study dosing period

Throughout the study medication dosing period, subjects may not receive any of the following concomitant medications:

- Immunomodulating agents (including immunosuppressive agents, interferon or other immune or cytokine-based therapies), and/or systemic chemotherapeutics;
- Chronic treatment with immune-suppressive therapy (stable use of asthma inhalers and topical corticosteroids are permitted);
- Subjects also should not receive any other vaccines during their participation in this study;
- Other investigational drugs.

NSAID and steroid therapy (e.g. intra-articular joint injection or daily oral prednisone at > 10 mgs/day) may be utilised, if required, after Day 29 of the study. Subjects can receive prednisone at < 10 mgs/day either stably or intermittently during the study.

All concurrent medications, including vitamin supplements and herbal remedies, must be recorded in the appropriate section of the CRF.

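### The steroid look-back in exclusion 3 runs from screening, not first dose, so a prednisone course above 10 mg/day completed before Day 1 is admitted and can distort the Day 1 baseline

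*Protocol*

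**What the plan says.** Exclusion 3, worded alike in the synopsis and in 6.3, excludes patients "Currently receiving or have received treatment with >10mg prednisone daily within the last 2 weeks prior to screening". The matching bullet in 9.2.1 has no look-back: "Currently receiving >10mg prednisone/day".

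On timing, 7.3.1 states: "Subjects will be screened within 35 days prior to randomisation to determine eligibility for participation in the study". Table 1-1 agrees (Day -35 to -1). The synopsis has "Screening: Up to 21 days".

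At Visit 2, before dosing, 7.3.2 lists "Review of inclusion/exclusion criteria (see Section 6.2 and 6.3").

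Methotrexate stability in 6.2 is counted differently: "Treatment with MTX at the same dose for at least 2 weeks prior to planned start of trial treatment". The DMARD bullet in 9.2.1 counts its 2 weeks to trial commencement.

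During the study, 9.2.2 says: "NSAID and steroid therapy (e.g. intra-articular joint injection or daily oral prednisone at > 10 mgs/day) may be utilised, if required, after Day 29". Prednisone below 10 mg/day is allowed throughout, stably or intermittently. The prohibitions in 9.2.2 are stated for the dosing period.

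**The concern.** A look-back protects a baseline only if it reaches the baseline. This one is fixed to a visit that may precede Day 1 by weeks, and RA patients may be treated for a flare in between.

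Three results depend on the Day 1 value:
- DAS28CRPv4 is used to judge RA exacerbation, within the primary safety endpoint, and its mean change from baseline is a secondary endpoint (4.2).
- The immunomodulation endpoint is the mean change in T-cell proportion and phenotype from before to after dosing (13.6.2). Table 1-1 places tetramer samples on Days 1, 8 and 29 only, so no screening sample can stand in for an affected Day 1.
- Part A safety and immunomodulation data inform the choice of the two Part B doses (13.8), with 4 active patients per dose level.

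If a steroid course has lowered disease activity on Day 1 and the effect then fades, the later rise looks like worsening after study drug. A similar artefact is possible in the T-cell readouts, although the protocol gives no figure for it.

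**Working it through.** **1. Days the look-back leaves uncovered.** If screening is on Day -s, the look-back covers about Day -(s+14) to Day -s and leaves s days before Day 1.

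| Screening limit | Look-back covers | Uncovered before Day 1 |
|---|---|---|
| 35 days (7.3.1, Table 1-1) | Day -49 to Day -35 | up to 35 days |
| 21 days (synopsis) | Day -35 to Day -21 | up to 21 days |

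Whenever s exceeds 14, the look-back covers none of the 2 weeks just before Day 1. The gap exists under either screening length.

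**2. Does another rule close it?** Take a course above 10 mg/day begun after screening and stopped before Day 1.
- Exclusion 3, current use: not met on Day 1, because the course is over.
- Exclusion 3, look-back: not met, because the course came after screening.
- 9.2.1, steroid bullet: not met, because it covers current use only.
- 9.2.2: does not apply before dosing.
- Exclusion 10 (immunomodulatory therapies): its examples name no corticosteroid, and prednisone has its own criterion.
- Concurrent medication recording (section 9): the course would be recorded, but recording does not exclude.

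The patient is eligible. The same holds for a joint injection before entry, since no eligibility text names that route. A patient still taking more than 10 mg/day on Day 1 is caught by the Visit 2 review.

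**3. Size, as an illustration.** The protocol has no sample size calculation and no DAS28 standard deviation, so it offers no figure on this point to reproduce. The Appendix 2 formula and worked example (tender 14, swollen 1, CRP 10 mg/L, general health 75 mm) serve as a test case:

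0.56×√14 + 0.28×√1 + 0.36×ln(11) + 0.014×75 + 0.96 = 2.095 + 0.280 + 0.863 + 1.050 + 0.960 = 5.25, as Appendix 2 states.

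Assumption, not from the protocol: the course lowers all four components by 20% to 50%.
- 20% lower: 1.874 + 0.250 + 0.791 + 0.840 + 0.960 = 4.72, a fall of 0.53.
- 50% lower: 1.482 + 0.198 + 0.645 + 0.525 + 0.960 = 3.81, a fall of 1.44.

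Assume also that the effect has gone by follow-up. One such patient then moves the arm's mean change upward by fall/n:

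| Arm | n | 0.53/n | 1.44/n |
|---|---|---|---|
| Part A active, one dose level | 4 | 0.13 | 0.36 |
| Part B placebo, one group | 5 | 0.11 | 0.29 |
| Part B placebo, both groups pooled | 10 | 0.05 | 0.14 |
| Part B active, one group | 15 | 0.04 | 0.10 |

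Section 11 keeps the SMC blinded. If it sees a Part A cohort of 6 without a split by arm, the shift is 0.09 to 0.24. No size can be given for the T-cell readouts.

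**The case against.** The strongest reply is that the trial is randomised and blinded and its analysis is descriptive (13.1). Pre-dose steroid use does not depend on allocation, so on average it affects DEN-181 and placebo alike and does not bias their comparison. That stands. It does not protect the pre/post comparison within the DEN-181 group, which the synopsis also plans, and balance on average is weak protection in arms of 4 or 5.

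Second, exposure would be visible: medication is recorded at every visit and DAS28CRPv4 is scored at both screening and Day 1. That stands for DAS28. It does not help the tetramer data, which have no earlier sample. A sensitivity analysis in the SAP could set affected patients aside but could not recover their baseline.

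A reader might also infer more than the protocol supports:
- **A gap of about 70 days after rescreening.** 7.3.1 lets earlier clinical data be reused, but updated for medications, and the new 35-day window may be read as a new screening. Adding the ±3-day screening window of 7.2 to reach 38 days is also debatable, since 7.3.1 gives 35 days as the limit.
- **An intended two-week steroid-free period that shrinks to none.** The protocol never asks for steroid-free patients, since it allows prednisone below 10 mg/day throughout. No passage states an intended interval before Day 1.
- **One criterion out of step with a uniform Day 1 rule.** Anchors are mixed. Exclusion 4 in 6.3 gives none, exclusions 5 and 7 refer to the last 28 days, and exclusion 6 refers to entry. The contrast is with methotrexate in 6.2 and the DMARD bullet in 9.2.1.
- **Distortion as a fact.** The protocol gives no frequency of steroid use and no size or timing of any effect.

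**Conclusion.** The gap in the text is real. Followed exactly, the protocol admits a patient who took more than 10 mg/day of prednisone after screening and stopped before Day 1, and it has no named pre-entry rule for joint injections although 9.2.2 allows them only after Day 29. The interval without a look-back is up to 35 days, or 21 on the synopsis figure.

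Such exposure can distort the Day 1 baseline; whether it will is unknown. Per affected patient, the shift in mean DAS28CRPv4 change is modest in a Part B active group and larger in the small arms. These figures rest on the assumed 20% to 50% fall, on the Appendix 2 example as a typical patient, and on the effect having worn off by follow-up. If the effect lasted through follow-up, the shift would be smaller. The exposed results are within-arm changes and chance imbalance in small groups, including the Part A data used to choose Part B doses. The expected difference between DEN-181 and placebo is not biased.

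**What to change.** Count the existing look-back in exclusion 3 to the first dose, the anchor that 6.2 already uses for methotrexate ("prior to planned start of trial treatment"). Make the change in the synopsis, in 6.3 and in the steroid bullet of 9.2.1, and have it checked explicitly at the Visit 2 eligibility review. This moves only the date from which the existing 2 weeks are counted.

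Separately, reconcile 6.3, 9.2.1 and 9.2.2 on steroid agents, routes and limits. Joint injection appears only in 9.2.2, and exactly 10 mg/day falls between the limit above 10 in 6.3 and the allowance below 10 in 9.2.2. Reconcile also the 21-day and 35-day screening periods. Which agents, routes, limits and intervals apply is for the sponsor's clinicians.

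The cost is a wording change and an occasional postponed Day 1, with the repeat haematology, chemistry and pregnancy tests that 7.3.1 already provides for if the 35-day window lapses.
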